- t) Patients will have blood samples drawn predose and at 1 hour and 2 hours (± 15 min) postdose on Cycle 1, Day 1 and Cycle 2, Day 1 for sparse PK sampling and time-matched concentration-ECG analysis. Blood samples will be collected at Cycle 3 Day 1 and then every 8 weeks in order correlate pozotinib concentrations with plasma ctDNA and efficacy; the time of the last dose and the time of blood draw should be recorded. In addition, if a patient presents with a potentially drug-related Grade ≥ 3 TEAE (e.g., rash, mucositis, diarrhea, pneumonitis), blood samples will be collected as soon as possible following the onset of the AE and the time of the last dose and the time of blood draw should be recorded.
- u) Pozotinib will be dispensed on Day 1 of each cycle. Pozotinib should be taken with food and a glass of water (approximately 240 mL) at approximately the same time(s) each day.
- v) During the Screening Period, only SAEs will be recorded. All AEs will be collected from Cycle 1, Day 1 through the Safety Follow-up Visit.
- w) Concomitant medications will be collected at Day 1 of each cycle, Day 8 and Day 15 during Cycle 1, and at the Safety Follow-up Visit.
- x) Telephone contact will be made to collect AE and concomitant medication information from patients on Cycle 1, Day 22, every week in Cycle 2, and **Day 15 (± 2 days)** in each cycle thereafter. During the long-term follow-up patients will be contacted every 3 months to assess survival.

Pozotinib Dosing Recommendations

In Phase 1 of the study (Dose-Finding), dosing modifications are not allowed during Cycle 1 but are allowed beginning with Cycle 2. Dosing modifications are allowed at any time during Phase 2 of the study. Dosing modifications are described in the table below. If needed, doses will be reduced by 2 mg/dose (i.e., if on QD, the reduction will be a total of 2 mg/day or if on BID, the reduction will be a total of 4 mg/day), regardless of starting dose, and will be at the Investigator's discretion; the Sponsor should be notified. Dose modifications not described in the table below must be discussed with Medical Monitor for approval. After dose reductions, if the patient has a documented confirmed progression, the patient's dose can be increased up to the starting dose.

Recommendations for Dose Reductions after Cycle 1 in Phase 1 and During Phase 2

Related Adverse Event	Triggering Criteria	First Occurrence	Subsequent Occurrences

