Diarrhea	Grade ≥ 3 (Despite optimal anti-diarrhea management)	Stop pozotinib treatment until the AE has improved to Grade ≤ 1 and then continue treatment at the same dose. or Reduce pozotinib dose by 2 mg/dose	Reduce pozotinib dose by 2 mg/dose
	Grade ≥ 2 for ≥ 48 hours (Despite optimal diarrhea management)		
Fatigue	Grade ≥ 3		
Mucositis/Stomatitis	Grade ≥ 3 (Despite optimal management)		
Nausea and/or Vomiting	Grade ≥ 3 (Despite optimal anti-emetics)		
	Grade ≥ 2 for ≥ 48 hours (Despite optimal anti-emetics)		
LVEF Dysfunction	Grade ≥ 3		
Rash	Any Grade	Refer to Rash Management Recommendations (Appendix 4)	
Pneumonitis	Grade 1	Stop pozotinib treatment, assess pulmonary function, and monitor the patient as clinically indicated. Contact the Sponsor to discuss continuing treatment, if resolved.	Discontinue Treatment
	Grade ≥ 2	Discontinue treatment. Assess pulmonary function and monitor the patient as clinically indicated.	NA

Dose interruptions should be minimized in order to reduce the risk of progression. Supportive medications, including early steroid use, should be considered even in the presence of low-grade "on-target" toxicity (eg, rash, diarrhea). The respiration and pulmonary function of the patient will be assessed throughout Cycle 1. Interstitial lung disease (ILD) is a clinical diagnosis and if

in the opinion of the Principal Investigator the patient has developed signs or symptoms of Grade ≥ 2 pneumonitis (CTCAE Version 5.0), the patient would stop dosing and depending on the response/recovery may be discontinued from the study. If the patient has developed signs or symptoms of Grade 1 pneumonitis, the Investigator can stop treatment after consultation/discussion with the Medical Monitor.

TABLE OF CONTENTS

TITLE PAGE	1
INVESTIGATOR SIGNATURE	2
SYNOPSIS	3
TABLE OF CONTENTS	19
List of Tables	21
List of Figures	21
1 INTRODUCTION	23
1.1 Background	23
1.1.1 Human Epidermal Growth Factor Receptor Family and Cancer	23
1.1.2 Pozotinib	24
1.1.3 Pozotinib Clinical Studies	32
1.2 Rationale for the Current Study	36
2 STUDY OBJECTIVES	38
2.1 Primary Objective	38
2.2 Secondary Objectives	38
2.3 Exploratory Objective	38
3 INVESTIGATIONAL PLAN	39
3.1 Study Design and Treatment Plan	39
3.1.1 Phase 1: Dose-Finding	39
3.1.2 Phase 2: Efficacy	40
3.2 Study Duration	43
4 PATIENT POPULATION	43
4.1 Inclusion Criteria	43
4.2 Exclusion Criteria	44
4.3 Patient Discontinuation/Withdrawal Criteria	45
5 STUDY PROCEDURES	46
5.1 Screening	46
5.2 Patient Assignment	46

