4.3 Patient Discontinuation/Withdrawal Criteria

Patients can withdraw from participation in this study at any time, for any reason, specified or unspecified, and without prejudice.

All treated patients must be withdrawn from study drug administration for the following reasons:

- Development of an adverse event (AE) that interferes with the patient's participation
- Initiation of non-protocol therapy
- Development of progressive disease (PD)
- Patient withdrawal of informed consent
- Delay of pozotinib administration for > 28 days since last pozotinib administration
- Investigator decision
- Sponsor decision

- Lost to follow-up
- Pregnancy
- Death

The reason for the patient discontinuing study treatment or terminating from the study must be recorded on the case report form (CRF). Patients who discontinue treatment or who are withdrawn from treatment will return for a Safety Follow-up Visit 35 (± 5) days after the last dose of pozotinib or prior to beginning a new treatment, whichever is first. If death is recorded as the reason for study discontinuation, the cause of death should be recorded on the CRF.

After study drug discontinuation, patients who have consented will be contacted every 3 months, for up to 2 years after patient's first dose of pozotinib, for survival assessment.

All patients will be withdrawn from the Long-Term Follow-up for the following reasons:

- Patient withdrawal of informed consent
- Investigator decision
- Sponsor decision
- Lost to follow-up
- Death

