5.4.12 Cardiac Ejection Fraction

Cardiac ejection fraction will be assessed by either echocardiogram or multi-gated acquisition (MUGA) scan at Screening, and the Investigator can order subsequent tests based on patient standard of care. Results within 6 months prior to Cycle 1, Day 1 is acceptable if there is no major known cardiac event during this period.

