6.7 Pozotinib Dose Modification Recommendations

In Phase 1 of the study (Dose-Finding), dosing modifications are not allowed during Cycle 1 but are allowed beginning with Cycle 2. Dosing modifications are allowed at any time during Phase 2 of the study. Dosing modifications are described in [Table 3](#). If needed, doses will be reduced by 2 mg/dose (i.e., if on QD, the reduction will be a total of 2 mg/day or if on BID, the reduction will be a total of 4 mg/day), regardless of starting dose, and will be at the Investigator's discretion; the Sponsor should be notified. Dose modifications not described in the table below must be discussed with Medical Monitor for approval. After dose reductions, if the patient has a documented confirmed progression, the patient's dose can be increased up to the starting dose.

Table 3 Recommendations for Dose Reductions after Cycle 1 in Phase 1 and During Phase 2

Related Adverse Event	Triggering Criteria	First Occurrence	Subsequent Occurrences
Diarrhea	Grade ≥ 3 (Despite optimal anti-diarrhea management)	Stop pozotinib treatment until the AE has improved to Grade ≤ 1 and then continue treatment at the same dose. or Reduce Pozotinib Dose by 2 mg/dose	Reduce pozotinib dose by 2 mg/dose
	Grade ≥ 2 for ≥ 48 hours (Despite optimal diarrhea management)		
Rash	Grade ≥ 3 (Despite adequate anti-rash management)		
Fatigue	Grade ≥ 3		
Mucositis/ Stomatitis	Grade ≥ 3 (Despite optimal management)		
Nausea and/or Vomiting	Grade ≥ 3 (Despite optimal anti-emetics)		
	Grade ≥ 2 for ≥ 48 hours (Despite optimal anti-emetics)		
Rash	Any Grade	Refer to Appendix 4	
LVEF Dysfunction	Grade ≥ 3	Discontinue Treatment	NA
Pneumonitis	Grade 1	Stop pozotinib treatment, assess pulmonary function, and monitor the patient as clinically indicated. Contact the Sponsor to discuss continuing treatment, if resolved.	Discontinue Treatment
	Grade ≥ 2	Discontinue treatment. Assess pulmonary function and monitor the patient as clinically indicated.	NA

Abbreviation: NA = not applicable.

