8.6.1 Safety and Adverse Events

Safety will be assessed by reported/elicited AEs, laboratory assessments including hematology and chemistry, vital signs, physical examination, and neurological examination. The assessment of treatment-emergent AEs (TEAEs) includes SAEs, AEs leading to study drug discontinuation, and AEs related to the study drug.

The overall incidence of treatment-emergent AEs (TEAE) (ie, AEs occurring from the time the first dose of the study drug until 35 (\pm 5) days after the last dose) and the proportion of patients who discontinue because of a TEAE are the primary safety outcome measures. The number and percent of patients with new-onset TEAEs will be summarized by the MedDRA system-organ-class (SOC) level and Preferred Term for all treated patients, for each cohort. The summary of TEAEs will be presented in the following categories:

- Number and percentage of patients with any TEAEs by SOC and Preferred Term.
- Number and percentage of patients with any SAEs by SOC and Preferred Term.
- Number and percentage of patients with related TEAEs by SOC and Preferred Term.
- Number and percentage of patients with TEAEs causing discontinuation of the study by Body System and Preferred Term.

In addition, the number and percent of patients with TEAEs by grade will be summarized. Serious adverse events reported prior to treatment but after IC will be provided in a listing.

The number of completed cycles will also be summarized and analyzed descriptively.

All laboratory abnormalities will be classified according to CTCAE version 5.0 and summarized by toxicity grade.

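### The two current copies of the dose-modification table disagree on Grade 3 or higher LVEF dysfunction: Section 6.7 stops treatment permanently, while the synopsis has no stop and reads as allowing re-treatment

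*Combined protocol and SAP*

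**What the plan says.** The protocol contains two dose-modification tables with the same title, covering Phase 1 after Cycle 1 and all of Phase 2.

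- **Section 6.7, Table 3.** LVEF dysfunction has its own entries, placed after the any-grade rash row: "LVEF Dysfunction Grade ≥ 3 Discontinue Treatment NA". The first occurrence ends treatment, so no action is needed for a later one.
- **Synopsis, Pozotinib Dosing Recommendations.** The row reads only "LVEF Dysfunction Grade ≥ 3". It comes directly after nausea/vomiting and before rash, and both action cells are blank. The last first-occurrence action stated above it is "Stop pozotinib treatment until the AE has improved to Grade ≤ 1 and then continue treatment at the same dose", or alternatively a reduction of 2 mg per dose. For later occurrences the action is a 2 mg per dose reduction.

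The synopsis presents its own copy as the working one: "Dosing modifications are described in the table below". For anything the table leaves out it says: "Dose modifications not described in the table below must be discussed with Medical Monitor for approval".

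Section 4.3 lists general withdrawal reasons, including an interfering adverse event, investigator or sponsor decision, and "Delay of pozotinib administration for > 28 days since last pozotinib administration". None is specific to LVEF. Section 5.4.12 schedules ejection fraction once, by echocardiogram or MUGA "scan at Screening, and the Investigator can order subsequent tests based on patient standard of care".

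**The concern.** This row is a stopping rule for a serious cardiac toxicity, and the two copies lead to different actions. Under Table 3 the patient never receives the drug again. Under the synopsis, a patient who recovers to Grade 1 or better within 28 days can be read as eligible to restart at the full dose, and a second event would call only for a dose reduction. The synopsis allows this without requiring it. However, the text around both tables advises keeping interruptions short, which leans towards restarting.

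There is also a smaller reporting consequence. Section 8.6.1 states that the overall TEAE incidence and "the proportion of patients who discontinue because of a TEAE are the primary safety outcome measures". Whether an LVEF event counts as a discontinuation would depend partly on which table the site followed.

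**Working it through.** The plan states no figure to reproduce here. The check is a comparison of the two tables, followed by simple arithmetic for scale.

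**Step 1: the rows side by side**

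| Feature | Synopsis table | Section 6.7, Table 3 |
|---|---|---|
| Position of LVEF row | After nausea/vomiting, before any-grade rash | After any-grade rash, before pneumonitis |
| First occurrence | Blank | Discontinue |
| Subsequent occurrences | Blank | Not applicable |
| Separate row for rash Grade 3 or higher | No | Yes |

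**Step 2: what the blank cells mean.** In both tables, fatigue, mucositis/stomatitis and nausea/vomiting also have blank action cells. They evidently share the diarrhea actions through merged cells. There are two readings of the synopsis LVEF row:

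1. It belongs to the same merged block. The action is then to hold to Grade 1 or better and resume at the same dose, or reduce by 2 mg per dose; on recurrence, reduce by 2 mg per dose.
2. It has no action. Under the synopsis's own rule, a modification not described in the table needs the Medical Monitor's approval.

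Neither reading yields discontinuation. The only discontinuation entries in the synopsis table are for pneumonitis.

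**Step 3: does other text settle it?** The synopsis is labelled Amendment 2, 04 Mar 2020, so it is current text and not a change log. No statement gives one copy precedence. The Section 4.3 rules are general, and the 28-day limit does not catch a patient who recovers sooner.

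**Step 4: could text have been lost when the tables were machine-read?** This is unlikely, for three reasons. The LVEF row stands in a different place in each copy, which dropped text would not explain. Both action cells would have to be missing while the nearby rash and pneumonitis cells survived. The separate row for rash Grade 3 or higher appears in only one copy, which suggests the two were edited separately.

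**Step 5: scale.** Inputs: 20 patients per Phase 2 cohort and 40 in Phase 2 (Section 8.1). The number of events, k, is an assumption because the documents give no LVEF incidence. Assume that all k events fall in one cohort, and that each counts as a TEAE discontinuation under one table but not under the other. The shift in the discontinuation proportion is then 100 × k/20 points for the cohort and 100 × k/40 points for Phase 2.

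| k (assumed) | One cohort | All of Phase 2 |
|---|---|---|
| 0 | 100 × 0/20 = 0 | 100 × 0/40 = 0 |
| 1 | 100 × 1/20 = 5.0 | 100 × 1/40 = 2.5 |
| 2 | 100 × 2/20 = 10.0 | 100 × 2/40 = 5.0 |

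Both tables also apply to Phase 1 patients from Cycle 2 onward, so the patients exposed to the inconsistency are not only these 40.

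**The case against.** The strongest objection is that the conflict is inferred from blank cells in a table read by a program. The same reading displaced cells elsewhere: the Phase 1 schedule of assessments appears twice, and its column headings do not line up between the two copies. Intact neighbouring cells do not prove that the LVEF cells are intact, and a different row order shows a different layout, not an empty cell. This stands as a reason to check the source file first. It does not make lost text the likelier explanation.

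Second, Table 3 is explicit and is the numbered table in the List of Tables, so a careful site would follow it. That is a fair guide to what was intended. But the synopsis says its own table describes the modifications, and no rule of precedence tells a site to look further.

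Third, there are safeguards. Investigator and sponsor can stop treatment at any time, patients with ejection fraction below 50% are excluded at Screening, the Medical Monitor reviews safety continuously, and both tables are titled as recommendations. On the second reading of the blank cells, the decision goes to the Medical Monitor. These lower the chance of harm, but none of them requires discontinuation.

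Fourth, the effect on results is small and hypothetical. LVEF dysfunction is absent from the common-event table, the events of special interest and the list of common adverse events. The discontinuation proportion is descriptive, with no threshold. All of this is correct. It limits how often the conflict would matter, but does not resolve it. It is also right that this looks like a mismatch between two copies and not a deliberate design decision.

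**Conclusion.** The concern holds. Two current tables with the same title and scope give different instructions for Grade 3 or higher LVEF dysfunction, and nothing in the protocol reconciles them. As written, the synopsis could lead a site to re-treat a patient whom Section 6.7 discontinues permanently.

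It must be fixed because of the kind of harm and the negligible cost of correction, not because of expected frequency. Few events are likely to be detected, since no ejection-fraction test is scheduled on treatment. Under the assumed counts of 0 to 2 events, the effect on a cohort's discontinuation proportion is 0 to 10.0 points. ORR and its confidence interval are unaffected.

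Confidence is moderate. The conclusion rests on the synopsis cells being blank in the source file as they are in the extracted text.

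**What to change.** Check the synopsis table in the source file. If the LVEF cells are blank or merged with the block above, do one of the following:

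- give the synopsis LVEF row its own entries matching Table 3: discontinue at first occurrence, not applicable thereafter; or
- remove the synopsis table and refer to Table 3 in Section 6.7. This also removes the mismatch in the rash rows.

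Either change is one table row or one cross-reference, made in an amendment or clarification letter. It adds no procedures or patients and changes no analysis.

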Dose interruptions should be minimized in order to reduce the risk of progression. Supportive medications, including early steroid use, should be considered even in the presence of low-grade “on-target” toxicity (eg, rash, diarrhea). The respiration and pulmonary function of the patient will be assessed throughout Cycle 1. Interstitial lung disease (ILD) is a clinical diagnosis and if in the opinion of the Principal Investigator the patient has developed signs or symptoms of Grade ≥ 2 pneumonitis (CTCAE Version 5.0), the patient would stop dosing and depending on the response/recovery may be discontinued from the study. If the patient has developed signs or symptoms of Grade 1 pneumonitis, the Investigator can stop treatment after consultation/discussion with the Medical Monitor.

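### For a first Grade 1 pneumonitis, the dose-modification tables say to stop pozotinib; the paragraph after each table makes the stop optional and puts it after a Medical Monitor consultation

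*Combined protocol and SAP*

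**What the plan says.** The pneumonitis rule is given twice, in the synopsis (Pozotinib Dosing Recommendations) and in Section 6.7. Each time there is a table followed by a paragraph.

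**Grade 1.** Both tables give the first-occurrence action as "Stop pozotinib treatment, assess pulmonary function, and monitor the patient as clinically indicated", and then "Contact the Sponsor to discuss continuing treatment, if resolved". A recurrence means discontinuing treatment. The paragraph after each table says that "the Investigator can stop treatment after consultation/discussion with the Medical Monitor".

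**Grade ≥ 2.** Both tables say "Discontinue treatment. Assess pulmonary function and monitor the patient as clinically indicated", with later occurrences marked not applicable. The paragraph says "the patient would stop dosing and depending on the response/recovery may be discontinued from the study".

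Two other sentences bear on the point. The text before each table says "Dose modifications not described in the table below must be discussed with Medical Monitor for approval". The paragraph itself opens with "Dose interruptions should be minimized in order to reduce the risk of progression".

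The title of Table 3 limits it to Phase 1 beyond the first cycle and to Phase 2. Section 3.1.1 bars dose modifications during Cycle 1 of Phase 1.

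**The concern.** An investigator who sees a first Grade 1 pneumonitis needs one answer to one question: is drug stopped now? The table says yes. The paragraph says it may be, after a conversation with the Medical Monitor. A site that relies on the paragraph could continue dosing and be within the protocol as written. A site that relies on the table would hold drug at once.

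The stake is patient safety. The sponsor evidently regards lung toxicity as a risk worth guarding against: Section 4.2 excludes anyone with current or past interstitial lung disease, and Section 5.4.4 schedules spirometry and oxygen saturation during treatment. Those checks find an event. The dose-modification text decides what is done about it, and that text gives two answers.

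**Working it through.** There is no figure to reproduce, so the check is a comparison of the texts. The synopsis and Section 6.7 agree with each other on pneumonitis. The conflict is between table and paragraph, and it occurs in both places.

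| Grade 1, first occurrence | Tables (synopsis; Table 3) | Paragraph after each table |
|---|---|---|
| Is drug stopped? | Yes, as an unconditional instruction | Permitted |
| When is the sponsor side consulted? | After the stop | Before the stop |
| What is the consultation about? | Continuing, if resolved | Stopping |
| Lung-function assessment | Part of the action | Not mentioned |
| Recurrence | Discontinue treatment | Not mentioned |

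The first three rows cannot all be satisfied together. The last two are omissions: the paragraph does not repeat those steps, but it does not cancel them either.

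I then looked for anything in the protocol that would settle the matter.

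1. *A precedence statement.* There is none in the synopsis or in Section 6.7.
2. *The approval sentence* ("Dose modifications not described in the table below must be discussed with Medical Monitor for approval"). It covers modifications that the table does not describe. Grade 1 pneumonitis is described in the table, and carrying on at the same dose is not obviously a modification. The sentence does not clearly catch a site that continues.
3. *Scope by cycle.* The sentence before the pneumonitis sentences says respiration and lung function are assessed throughout Cycle 1. The pneumonitis sentences carry no such limit, and Cycle 1 of Phase 2 lies within the tables' scope in any case. Both texts therefore apply to Phase 2 and to Phase 1 from Cycle 2.
4. *Scope by causality.* The tables are headed for related events, while the paragraph speaks of signs or symptoms with no condition on relatedness. A drug-related Grade 1 event still falls under both, so the conflict remains for exactly the events the table is about.
5. *Meaning of the word stop.* It might mean permanent discontinuation in the paragraph. The table uses the same verb for an immediate hold that may be lifted. Even on the permanent reading, the paragraph leaves out the hold.

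For Grade ≥ 2 the texts can be reconciled. Section 4.3 treats leaving treatment and leaving the study as separate events: "The reason for the patient discontinuing study treatment or terminating from the study must be recorded". On that basis the paragraph can mean that drug stops and only study participation depends on recovery, which agrees with the tables. The reference to response and recovery still leaves room for another reading, so the wording should be tightened. It is secondary to the Grade 1 conflict.

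**The case against.** The best case against is that this is loose drafting with other safeguards around it. The tables are titled as recommendations, so to say they strictly require a stop is a little strong. Monitoring is frequent: Day 1 of every cycle includes oxygen saturation, a complete physical examination and chemistry with KL-6 and C-reactive protein. Section 4.3 allows withdrawal for an interfering adverse event. In Phase 1, a patient who does not pass the Section 5.3.3 evaluations, which include lung checks, stays in hospital under Section 5.3.4 until the discharge criteria are met or the cycle ends. The opening line about keeping interruptions few ("Dose interruptions should be minimized in order to reduce the risk of progression") is followed by a sentence on rash and diarrhea as examples of low-grade on-target toxicity, so it is weak evidence that sites would be pushed to dose through pneumonitis.

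Most of this stands, and it limits how serious the consequence is likely to be. It does not remove the conflict. A recommendation to stop first and a permission to stop after consultation still differ, and monitoring does not say which action to take.

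A reader might infer three stronger things that the documents do not support:

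- *That the paragraph authorises rechallenge after Grade ≥ 2 pneumonitis.* It can be read consistently with the tables through Section 4.3, so it is an ambiguity and not a second contradiction.
- *That the same conflict exists in Phase 1 Cycle 1.* The tables do not apply there, so there is nothing for the paragraph to contradict. What exists is a scope gap.
- *That a number of patients is at risk.* The documents give no pneumonitis rate for pozotinib, and enrolment totals are not a measure of harm.

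**Conclusion.** The point holds for a first Grade 1 pneumonitis in Phase 2 and in Phase 1 from Cycle 2. The tables give an unconditional stop with Sponsor contact about continuing; the paragraphs give an optional stop after Medical Monitor contact; nothing ranks them. It is an internal inconsistency in a stop-drug safety instruction, present in both the synopsis and Section 6.7.

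Its size is one instruction stated inconsistently in two places. How often it would matter cannot be estimated from the documents. How ORR is defined, analysed and sized does not depend on it. The conclusion assumes only that a site may treat the paragraph as operative text, which its placement directly after the table invites. It is worth correcting because the sponsor's own table already contains the safer rule.

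**What to change.** Make the same change in the synopsis paragraph and in the Section 6.7 paragraph.

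- **Grade 1:** replace the sentence with the table's action. Stop pozotinib, assess pulmonary function and monitor as clinically indicated. Contact the Sponsor about continuing only if the event has resolved. Discontinue treatment on recurrence.
- **Grade ≥ 2:** state that pozotinib treatment is discontinued, with pulmonary function assessed and monitoring as clinically indicated. Let only study participation (follow-up) depend on recovery.

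**Phase 1 Cycle 1** needs a separate decision by the sponsor, because extending the tables into that cycle would be a new design choice set against the bar in Section 3.1.1. The protocol should say whether a pneumonitis hold is allowed there. If it is, the protocol should also say whether the held patient remains evaluable for DLT or is replaced. Grade 1 pneumonitis is below the Grade 3 non-hematological DLT threshold, and Section 8.1 addresses replacement only for patients who discontinue before completing the cycle for reasons other than a DLT.

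The cost is a wording amendment. Under the undertaking on the investigator signature page it needs IRB/EC approval before it is implemented. Aligning the two paragraphs adds no patients or procedures; a decision to allow holds in Phase 1 Cycle 1 could add replacements, depending on the evaluability rule chosen.
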